The primary outcomes of this trial were to ascertain 1. The safety and AZM pharmacokinetic and 2. If treatment with AZM resulted in decreased nasal MMP-9 levels. Notably, when the study protocol was expanded to include non-ventilated patients, the primary outcome also changed from endotracheal MMP-9 to nasal MMP-9 levels. The secondary outcomes were to determine the *in vivo* efficacy of AZM administration on improving clinical outcome measures, specifically duration of ventilatory support and oxygenation, as well as PICU and hospital length of stay. The CONSORT guideline was used for the reporting of this trial.

Visit Schedule and Study Procedures

Overview:

If subjects met the inclusion criteria and have no contraindication to study participation, they were be enrolled into the study within 48 hours of positive pressure ventilation. Subjects were randomized via a permuted block design to receive either placebo (normal saline), 10mg/kg of IV azithromycin or 20 mg/kg of IV azithromycin, daily for 3 days. Prior to drug administration, assessment was performed to ensure that subjects do not have contraindications of AZM administration or development of any adverse events. Nasal and endotracheal aspirate (if

intubated) were obtained daily for the first 3 days (first sample obtained before drug administration).

Prior to drug administration, baseline labs (CBC with differential, liver and renal function, electrolytes) was reviewed. If the patient had evidence of hypokalemia, hypocalcemia or hypomagnesemia, the electrolyte abnormalities were corrected prior to drug administration. EKG was also reviewed, and if there was evidence of prolonged QT, the subject was excluded from the study. Vital signs (heart rate, blood pressure, temperature, saturations), ventilator or BiPAP or HFNC settings, presence of multi-organ failure were recorded. All these parameters were assessed prior to drug administration. Vital signs (heart rate, blood pressure, temperature, saturations) were also assessed immediately before the drug infusion, during, and 2 and 4 hours post completion of infusion.

During the hospitalization, all patients were treated according to the American Academy of Pediatrics guidelines for the management of bronchiolitis, namely supportive care. All decisions regarding medical treatment during hospitalization were made by the patient's primary care team.

Data Collection:

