Nasal, endotracheal aspirates (if intubated) and serum samples were obtained once daily for the first 3 days. The collection window had at least 24 hours between each sample collection. If patients were extubated within the first 3 days of study window, only nasal samples will be collected. Clinical data was collected each day until the subject was discharged from the ICU.

An overview of clinical and biologic data is outlined in this table.

	Day 1	Day 2	Day 3	Day of PICU discharge	Day of hospital discharge
AZM level (serum, nasal, lung)	X	X	X		
RSV titer (nasal and lung)	X	X	X		
Active MMP-9, Total MMP-9, TIMP (nasal and lung)	X	X	X		
Other RSV cytokine activity (nasal and lung)	X	X	X		
Continous vital signs monitoring ¹	X	X	X		
Baseline and continous lab review ²	X	X	X		
Electrocardiogram	X	X	X		
Study drug administration ³	X	X	X		
Duration of positive pressure ventilation (MV, BiPAP, HFNC)	X	X	X	X	X
Duration of oxygenation	X	X	X	X	X
Duration of PICU stay				X	
Duration of hospital stay					X

¹All assessments were done prior to dosing, during dosing until completion of infusion, immediately at the end of infusion, 2 and 4 hours post completion of infusion.

²Laboratories that were collected: CBC with differential, electrolytes, liver and renal function; record if done for clinical care.

³Study drug administration took place on 3 consecutive days (1 dose per day) after consenting. Study drug at 2 mg/ml was administered over 60 minutes.

Withdrawal of Participant Consent and Discontinuation of Study Drug:

Study participation may be discontinued for any of the following reasons:

- a. Subject decision to withdraw consent for study
- b. Evidence of allergy to administered products
- c. Intolerable adverse event as judged by study investigator

Safety Data

Adverse Events:

- a. Adverse event: Any untoward medical occurrence in a patient or clinical investigation in which a subject is given a pharmaceutical product; does not necessarily have a causal relationship with such treatment, or
- b. Any unfavorable and unintended sign (including abnormal laboratory findings), symptom, or disease temporally associated with the use of a medicinal (investigational) product; not necessarily related to the product.
- c. Change-from-baseline

AEs can take 2 forms:

- i. Appearance of a new symptom or sign, or
- ii. Increased severity or frequency of an existing symptom or sign

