All participant data were obtained and recorded in individual files that was stored in a secured file cabinet within a locked office. Upon study entry, all participants were given a unique identifier to be used through the entirety of the study and this too was maintained in a locked file cabinet in secured office. Following each study visit, the data obtained was entered into a database using the study participants' unique identifiers. All other personal data were omitted from electronic records. At the close of the study, any missing data was verified with chart review. Only authorized study personnel have access to patient data.

Data Analysis

The primary outcome measured was MMP-9 activity. Based on our preliminary data, we expect that n=16 per group would be sufficient to detect a 20% and 25% decrease in MMP-9 activity in the treated group (10mg/kg and 20mg/kg; respectively) relative to placebo with 80% power.

[name] (Professor, UAB School of Public Health) is the biostatistician for this clinical trial.

Nasal and Endotracheal Aspirate Collection and Processing

Nasal samples were collected using a nasal swab inserted through the nares parallel to the palate (not upwards) until resistance was encountered or the distance inserted was equivalent to that from the nostril to the ear of the patient indicating contact with the nasopharynx. After gentle rubbing and rolling of the swab, it was left in place for several seconds to absorb secretions prior to removal. The swab was then immediately placed into a sterile vial containing 3 ml of viral transport media (Quidel, San Diego, CA), and kept at 4°C for further analysis.

Endotracheal aspirates were collected via endotracheal tube suctioning using an 8 Fr suction cannula (CareFusion, San Diego, CA, USA) and centrifuged at 500xg for 10 min to separate supernatant from cells and mucus (pellet) . Separate aliquots of supernatant were subsequently saved at 4°C for further analysis.

Assay of AZM, Urea and Pharmacokinetic Analysis

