AZM and urea levels in tracheal aspirates and plasma samples were measured using liquid chromatography-tandem mass spectrometric assays. For quantitation of AZM, all samples were treated with 200 µL of acetonitrile containing terfenadine (5 ng/mL) as an internal standard. Samples were then vortexed briefly and centrifuged at 20,000xg for 5 minutes. The supernatant was transferred to autosampler vials for analysis. Detection was performed using an Applied BioSystems 4000 QTRAP (Applied Biosystems, Foster City, CA) triple quadrupole mass

spectrometer operated in the positive ion mode. Separation of AZM and the internal standard from the biological matrix was achieved using a Phenomenex Luna C18, 100 X 2 mm 5 μ m particle column. The mobile phase was delivered at a flow rate of 400 μ L/min using a gradient elution profile consisting of DI water with 0.1% formic acid (A) and acetonitrile with 0.1% formic acid (B). The AZM and internal standard were detected using multiple reaction monitoring (MRM) for the following transitions: AZM (m/z 749.6 \rightarrow 591.5), and Terfenadine (m/z 472.4 \rightarrow 436.3).

Samples (20 μ L) for urea analysis were prepared by diluting each sample matrix with 955 μ L of 90:10 acetonitrile:water followed by the addition of 25 μ L of internal standard (10 μ g/mL 4-aminobenzoic acid). The samples were vortexed, centrifuged and the resulting supernatant was transferred to autosampler vials and analyzed by LC/MS/MS. Separation of urea and the internal standard from the biological matrix was achieved using a Waters Spherisorb Silica, 150 X 3.2 mm 5 μ m particle column (Waters Corporation, Milford, MA). The mobile phase was delivered at a flow rate of 400 μ L/min using a gradient elution profile consisting of DI water with 0.1% formic acid (A) and acetonitrile with 0.1% formic acid (B). The urea and internal standard were detected using multiple reaction monitoring (MRM) for the following transitions: Urea (m/z 61.1 \rightarrow 44.1), and 4-aminobenzoic acid (m/z 138.1 \rightarrow 120.1).

Dilution estimations of recovered samples from endotracheal compartment were calculated using the urea dilution method. The following equation was used to calculate the corrected drug level in these samples:

$$AZM_{corrected} = \frac{Urea_{plasma}}{Urea_{matrix}} \times AZM_{measured}$$

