Where $\text{Urea}_{\text{matrix}}$ was the amount of urea in the endotracheal samples, $\text{Urea}_{\text{plasma}}$ was the amount of urea in the plasma of the corresponding patient, $\text{AZM}_{\text{measured}}$ was the measured amount of AZM in the matrix being assayed.

Peak plasma levels (C_{max}) and time to C_{max} (T_{max}) of AZM in all matrices were determined by visual evaluation of the concentration versus time profile. The AUC (area under the curve) values from 0 to 144 hours for each matrix was calculated using the trapezoidal rule. The half-life ($t_{1/2}$) of AZM in plasma and endotracheal samples were calculated as $\ln(2)/k_e$, where k_e is the terminal elimination rate constant estimated by linear regression analysis of the terminal portion of the concentration-time profile.

Penetration ratios for AZN in samples from the endotracheal compartment were calculated as $\text{AUC}_{\text{endotracheal}}/\text{AUC}_{\text{plasma}}$.

Biologic Outcome Measurement

Measurement of active MMP-9, total MMP-9 and Tissue Inhibitor of Metalloproteinase (TIMP)-1 was done using an established fluorometric assay (#F9M00 and #DTM100, respectively; R&D Systems, Calbiochem, Billerica, MA, USA). Interleukin (IL)-1, IL-2, IL-4, IL-6, IL-8, IL-10, IL-12, IL-13, tumor necrosis factor (TNF)- α , and interferon (IFN)- γ were analyzed via electrochemiluminescence using multi-array plates on a Meso Scale Discovery (MSD) Sector Imager 2400 (MSD, Gaithersburg, MD) using the MSD V-PLEX Cytokine Panel 1 Human Kit (No. K15049D-1, Rockville, Maryland, USA). All samples were processed as indicated by the manufacturer's protocol.

In brief, RSV loads were measured by reverse-transcription (RT) quantitative PCR using known concentrations of RSV to derive a standard curve. Standards and negative controls were included and tested with each PCR assay. RSV quantification was reported as log₁₀ copies/mL.

Clinical Data Assessment

The clinical data collected included duration of respiratory support, focusing on days of mechanical ventilation, non-invasive positive pressure ventilation via BiPAP or high flow nasal cannula, and total duration of supplemental oxygen. Other clinical data assessed included length of PICU and hospital stay. Co-morbidities such as history of prematurity, apnea, seizure disorder, chromosomal abnormalities, and the presence of multi-organ failure were identified.

Sample Size Determination and Statistical Analysis

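### Sampling once a day on Days 1 to 3 cannot supply the reported 0–144 h trapezoidal AUC or the terminal half-life

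*Combined protocol and SAP*

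**What the plan says.** **Sampling.** Data Collection states: "Nasal, endotracheal aspirates (if intubated) and serum samples were obtained once daily for the first 3 days". Samples are to be at least 24 hours apart. In the overview table, the azithromycin-level row is marked on Days 1, 2 and 3 and is blank at PICU and hospital discharge. Only clinical data continue to ICU discharge. Endotracheal sampling may end sooner: "If patients were extubated within the first 3 days of study window, only nasal samples will be collected".

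**Dosing.** Footnote 3 of that table puts the three daily doses on consecutive days, each infused over 60 minutes. The table marks them on the same Days 1 to 3.

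**Timing relative to dose.** The Overview under Visit Schedule and Study Procedures says the first nasal and endotracheal samples precede the drug. No dose-relative time is given for blood, or for any Day 2 or Day 3 sample.

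**Analysis.** The pharmacokinetic section reports: "The AUC (area under the curve) values from 0 to 144 hours for each matrix was calculated using the trapezoidal rule". Half-life in plasma and endotracheal samples is ln(2) divided by a "terminal elimination rate constant estimated by linear regression analysis of the terminal portion of the concentration-time profile". Cmax and Tmax are read by eye from the profile. The penetration ratio is endotracheal AUC over plasma AUC.

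**Status.** Primary and Secondary Outcomes lists "The safety and AZM pharmacokinetic" as the first primary outcome without naming parameters. Data Analysis, in contrast, says: "The primary outcome measured was MMP-9 activity".

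**The concern.** The trapezoidal rule joins observed concentrations and gives no area beyond the last one. A terminal slope needs at least two points, and usually three or more, after the final dose. On the written schedule neither condition is met, yet both parameters are reported.

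A reader therefore cannot tell which data lie behind the 72–144 h part of the AUC or behind the half-life, and can reproduce neither. A penetration ratio built on these AUCs inherits the problem. This bears on an outcome that the document calls primary.

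**Working it through.** **1. Timeline (no model needed)**

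- Doses on three consecutive days: nominally 0, 24 and 48 h.
- Samples once daily on Days 1 to 3: nominally 0, 24 and 48 h. The 24-hour spacing is only a minimum, so the third sample could be as late as the end of Day 3, 72 h. That upper limit is inferred.
- Unsampled part of the AUC window: (144 − 48)/144 = 96/144 = 67%, or (144 − 72)/144 = 72/144 = 50%.
- Samples after dose 3: none if the Day 3 sample is pre-dose, one if it is post-dose. A slope cannot be fitted to either.
- Samples 2 and 3 cannot stand in for a terminal phase. With one dose and one sample each day, at least one dose falls between them or after them.

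The 144 h limit cannot be reproduced from the schedule on either reading.

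**2. Illustration of the possible AUC error (assumptions, not document figures)**

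The document gives no half-life and no compartment model. Assume one compartment, 1-hour infusions starting at 0, 24 and 48 h, zero concentration before the first dose, and k = ln(2)/half-life. In units of dose/volume, a dose started u hours earlier contributes

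- (1 − e^(−ku))/k for 0 < u ≤ 1,
- [(1 − e^(−k))/k] × e^(−k(u−1)) for u > 1.

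The contributions of the three doses are added, and the true AUC(0–144) is found by numerical integration.

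Worked case, half-life 24 h, all samples pre-dose: C(0) = 0, C(24) = 0.507, C(48) = 0.761. Trapezoid = 24 × (0 + 0.507)/2 + 24 × (0.507 + 0.761)/2 = 6.08 + 15.22 = 21.30. The true AUC(0–144) is 100.03, so the ratio is 0.213.

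Columns 2 and 3 give the share of the true AUC(0–144) lying after 48 h and after 72 h. The remaining columns give trapezoid area divided by true AUC(0–144) for the sample times shown.

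| Assumed half-life (h) | After 48 h | After 72 h | 0, 24, 48 h (pre-dose) | 0, 28, 52 h | 4, 28, 52 h* | 0, 36, 72 h |
|---|---|---|---|---|---|---|
| 6 | 0.357 | 0.024 | 0.094 | 1.039 | 1.345 | 0.439 |
| 12 | 0.440 | 0.111 | 0.194 | 0.760 | 0.942 | 0.564 |
| 24 | 0.571 | 0.269 | 0.213 | 0.542 | 0.642 | 0.547 |
| 36 | 0.640 | 0.361 | 0.199 | 0.448 | 0.521 | 0.505 |
| 48 | 0.679 | 0.416 | 0.187 | 0.398 | 0.458 | 0.475 |
| 72 | 0.720 | 0.475 | 0.172 | 0.347 | 0.394 | 0.438 |
| 96 | 0.741 | 0.506 | 0.163 | 0.321 | 0.363 | 0.418 |

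*With an added zero at time 0. This pattern could apply only to blood, because the first nasal and endotracheal samples are stated to be pre-dose.

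**3. Illustration for the half-life**

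In the same model, take the slope between samples 2 and 3: apparent half-life = −ln(2) × (t3 − t2)/ln(C3/C2).

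- Both pre-dose (24 and 48 h): the concentration rises, so the apparent half-life is negative at every assumed value. With a true 24 h it is −24 × 0.693/ln(0.761/0.507) = −41 h.
- Post-dose at 26 and 51 h: about 155 h when the truth is 6 h, about 1,931 h when the truth is 12 h, and negative when the truth is 24 h or more.

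**The case against.** **The schedule may be what is wrong.** The text is in the past tense and dated after enrolment ended. An AUC to exactly 144 h may mean that later samples were taken and left out of the table. This stands: the document proves an inconsistency, not a faulty calculation. The blood samples offer mild support for incomplete description, since the schedule calls them serum while the assay section says: "AZM and urea levels in tracheal aspirates and plasma samples were measured".

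**The profile may have been pooled.** The document does not say whether profiles were individual or group. With varied sampling times across the 32 treated children (2 × 16), a pooled slope over roughly 48–72 h is conceivable. But no pooling is described, single samples within about a day of the third dose are not a documented terminal phase, and pooled data would still stop well short of 144 h. What stands is that the sponsor should say how the profile was built.

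**The simulated figures depend on their inputs.** This is correct. Samples at 0, 36 and 72 h recover 42–56% for half-lives of 12 to 96 h. With a 6 h half-life and post-dose samples, the trapezoid exceeds 100% (104% at 0/28/52 h, 126% at 0/26/51 h). Neither the size nor the direction of error is fixed, and a one-compartment plasma model need not describe endotracheal fluid. The contradiction itself does not rest on the model.

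**Reach is limited.** Cmax and Tmax read from a profile are already observed maxima, so what is missing there is mainly the sampling times. Power rests on MMP-9, and no test of a pharmacokinetic parameter is described.

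**Conclusion.** The concern holds. As written, the schedule does not support AUC(0–144) in any matrix, a terminal half-life, or a penetration ratio built on that AUC. A penetration ratio over a common sampled window remains computable where endotracheal samples exist.

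The size that follows from the text is 72 to 96 of 144 h (50–67%) without a scheduled sample, and at most one sample per child after the third dose. This assumes only nominal daily timing and sampling within Days 1 to 3. The error in the AUC cannot be determined from the document. Under the one-compartment assumption with half-lives of 24 to 96 h, 57–74% of AUC(0–144) lies after 48 h and 27–51% after 72 h. At 12 h the shares are 44% and 11%.

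Confidence is high that the passages conflict. Which of them is misdescribed cannot be settled from the document. This should be fixed because pharmacokinetics is listed as primary, but it does not touch the MMP-9, safety or clinical analyses.

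**What to change.** Reconcile the sampling schedule with the pharmacokinetic section.

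- **If later samples were taken:** correct the Data Collection text and table. Give actual sampling times relative to each dose, and state whether blood was serum or plasma. Say whether profiles were individual or pooled, and how many children and points support each terminal slope.
- **If not:** report observed concentrations and AUC over the sampled interval. Compute the penetration ratio over that same interval where endotracheal samples exist. Remove AUC(0–144) and the terminal half-life. Describe Cmax and Tmax as the observed maximum at the stated sampling times.

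The cost is wording in the table and the pharmacokinetic section, plus recalculation from existing assay results. If no later samples exist, fewer pharmacokinetic parameters can be reported.

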This study was designed to have a total sample size of 48 participants divided into three groups, with 16 per group to detect a 25% and 37.5% decrease in lung MMP-9 activity in the treated groups (10mg/kg and 20mg/kg, respectively) relative to placebo with 80% power using analysis of variance. The assumptions were based on MMP-9 levels found in endotracheal aspirate of children with RSV-induced respiratory failure (Kong et al, *ERJ* 2014).

Means, standard deviations, medians, quartiles and range (minimum, maximum) described continuous variables and counts and percentages for categorical variables. To compare baseline characteristics among the treatment groups, we used Kruskal-Wallis test for age, height and weight due to evidence of non-normality of the distribution of the values. We used either Chi-Square or Fisher's exact test for categorical variables depending on expected cell counts.

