We analyzed inflammatory markers by first performing \log_{10} transformation to address the skewness of the distribution and extreme outliers. We then calculated the difference at each time point relative to baseline to obtain the change (i.e. pre and post treatment) outcome and fitted a generalized linear mixed model (GLMM) with random intercepts and assumed unequal variances across treatment groups with change from baseline as the outcome. The model included treatment, day and treatment by day interaction. Point and confidence interval estimates of the mean change outcome at each time point and treatment group combination were obtained. If a confidence interval for the mean change does not include 0, this is evidence of an effect associated with that particular treatment as it is either a significant increase (or decrease) in the inflammatory marker relative to baseline. The Bonferroni approach was used to adjust for multiple testing and simultaneous confidence intervals. Thus, significance was determined using a cut-off of 0.002 and a 99.8% level was used to construct confidence intervals for each for each treatment at each time point. Note that the sample size justification was based on the assumption that the MMP-9 levels are normally distributed with common standard deviation. However, in the data for this trial, we observed evidence of non-normality and non-constant variance across the treatment groups. Thus, GLMM was deemed more appropriate than ANOVA. Furthermore, fitting GLMM allows us to combine unbalanced data from different time points to help gain more power in evaluating treatment effect.

We used a generalized linear model assuming a negative binomial distribution for clinical outcomes (measured in number of days), using log link to address possible overdispersion due to some extreme observations. Furthermore, we fitted a model that allowed the variance to differ by treatment group. Spearman Correlation was used to examine associations. For this set of

analyses, the standard 5% level of significance and 95% confidence interval was used as these are all exploratory outcomes. All analyses were done using SAS version 9.4.

IRB and IND

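### The 80% power behind N=48 is for lung MMP-9 in an all-intubated design, and was not updated when non-intubated children were admitted and the primary outcome became nasal MMP-9

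*Combined protocol and SAP*

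**What the plan says.** All of this is in the combined protocol and SAP.

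- **Sample Size Determination and Statistical Analysis.** The trial has 48 children in three groups, with "16 per group to detect a 25% and 37.5% decrease in lung MMP-9 activity" at the lower and higher dose "relative to placebo with 80% power using analysis of variance". On the source of the inputs: "The assumptions were based on MMP-9 levels found in endotracheal aspirate of children with RSV-induced respiratory failure". No SD and no significance level are given.
- **Eligibility/Inclusion Criteria.** Non-invasive support (BiPAP or high-flow oxygen) qualifies as well as invasive ventilation.
- **Primary and Secondary Outcomes.** The change is disclosed: "when the study protocol was expanded to include non-ventilated patients, the primary outcome also changed from endotracheal MMP-9 to nasal MMP-9 levels".
- **Visit Schedule and Study Procedures (Overview) and Data Collection.** Endotracheal aspirate is taken only in intubated children. Data Collection adds: "If patients were extubated within the first 3 days of study window, only nasal samples will be collected". Its table still schedules lung MMP-9 on Days 1 to 3.
- **Duration of Study.** Enrolment ended at 48 subjects in all, not at 48 intubated subjects.

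**The concern.** Sixteen per group is the whole randomised arm. The 80% therefore needs a lung MMP-9 value from every child, yet the sampling rules exclude any child who is never intubated. The marker analysis uses change from baseline, so a child intubated at baseline but extubated before a later sample also drops out.

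Two things are at stake. A reader could weigh a null lung result against 80% power that it does not have. And nasal MMP-9, the current primary marker, which every child can provide, has no sizing statement that identifies it.

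**Working it through.** **Inputs from the document.** 16 per arm; three arms; relative means 1, 0.75 and 0.625 (falls of 0%, 25% and 37.5%); power 80%; ANOVA; normal values with a common SD.

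**Assumptions.** Overall F-test at 5%; equal numbers of lung results per arm; a range for the number intubated, which the document does not give.

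**Step 1: the plan's own figure.** Without an SD the 80% cannot be reproduced independently. It can only be inverted.

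- Mean of the three means: (1 + 0.75 + 0.625)/3 = 0.7917.
- Sum of squared deviations: 0.2083² + 0.0417² + 0.1667² = 0.0434 + 0.0017 + 0.0278 = 0.0729.
- With n per arm, power = P(F > Fcrit), where F is noncentral with 2 and 3n − 3 degrees of freedom and noncentrality λ = n × 0.0729/SD².
- Setting power to 80% at n = 16 gives SD = 0.3365 of the placebo mean, so λ = 16 × 0.0729/0.1132 = 10.3.

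**Step 2: fewer lung results at the same SD.**

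| Lung results per arm | λ | Fcrit (5%) | Power |
|---|---|---|---|
| 16 | 10.3 | 3.20 | 80% |
| 12 | 7.7 | 3.28 | 66% |
| 8 | 5.2 | 3.47 | 46% |
| 6 | 3.9 | 3.68 | 34% |
| 4 | 2.6 | 4.26 | 21% |

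Twelve, eight and four per arm correspond to 75%, 50% and 25% of each arm intubated. Because the SD is calibrated to the plan's own 80%, the pattern does not depend on knowing the true SD.

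**Step 3: other choices of test.**

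- Recalibrating at a 2.5% level gives 64% at 12 and 41% at 8.
- A two-sided 5% pairwise t-test, calibrated the same way, gives 67% at 12 and 48% at 8.

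**Step 4: unequal numbers.** With 24 lung results in total, 8/8/8 gives 46%. A split of 12/6/6 (placebo, lower dose, higher dose) gives 49%, and 6/8/10 gives 42%. Imbalance can move power either way, depending on which arms are short.

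**Step 5: distance from the SAP's analysis.** The SAP fits a mixed model to log10 change from baseline, with unequal variances and a 0.002 cut-off. The F-test of Step 1, at 16 per arm and the same SD but tested at 0.002, has about 35% power. This too is only an illustration, since the SAP's intervals are for change within each group.

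**The case against.** The strongest reply is that the sizing paragraph is history. It is in the past tense, the move to nasal MMP-9 is disclosed elsewhere, and the same section says the sizing rested on the "assumption that the MMP-9 levels are normally distributed with common standard deviation", that the data departed from this, and that a mixed model replaced ANOVA. Lung MMP-9 is no longer primary, and a non-primary marker needs no power guarantee. This largely stands. It is why the 80% should be relabelled rather than deleted: it is part of the only stated rationale for 48. It does not remove the gap, because the section revisits normality and variance but never the smaller number of lung results, and nothing marks the figure as superseded.

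A second reply is that pooling days in the mixed model gains power. The SAP does not quantify that gain, and repeated days add no lung data from children who were never intubated.

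A third is that the Data Analysis section covers the current primary outcome, since it states 80% power for MMP-9 activity at 16 per group. It names no compartment and no SD, and its effects (20% and 25%) differ from those in the sample size section. It cannot be taken as a nasal calculation, and the two statements need reconciling.

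It is also right that the power table describes a raw-scale 5% ANOVA, which is not the planned analysis, and that nothing has been miscalculated.

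Three stronger readings go beyond the documents. A reader might infer that the lung comparison is known to have some particular low power, but no count of intubated children is given. A reader might infer that the plan presents 80% as current power for lung results; the disclosed change of outcome tells against that. And a reader might infer that unequal intubated numbers necessarily lower power further; Step 4 shows otherwise.

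**Conclusion.** The point holds as a sizing statement left behind by a disclosed change of population and primary outcome. The direction is firm: any child without a usable lung result takes the lung comparison below the plan's 80%, and that figure survives only if all 48 children were intubated and gave the samples needed. Admitting non-intubated children makes this implausible, though no count rules it out. The size is conditional: 66% to 21% for 12 down to 4 lung results per arm, given a 5% overall ANOVA, equal numbers and a back-solved SD. These figures are illustrative and are not the power of the SAP's mixed model. The 80% does not carry over to nasal MMP-9 either, because its inputs are endotracheal. The correction is worth making but does not threaten the trial.

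**What to change.** 1. In Sample Size Determination and Statistical Analysis, label the 80% as the original all-intubated endotracheal ANOVA design. State that it applies neither to the lung results of the enrolled population nor to nasal MMP-9.
2. Report, per arm, the number of children with paired pre-dose and post-dose endotracheal samples, and the confidence-interval half-width at that number under the SAP's mixed model. The document post-dates enrolment, so a half-width is more useful than power recomputed after the fact.
3. State that lung comparisons are limited to intubated children and are not powered at 80%.
4. Give the corresponding precision or detectable difference for nasal MMP-9 with 16 per arm.

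Cost: wording and one recomputation. The stated lung figure becomes less favourable, and no patients are added.
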